2.2.3 Inferential statistics

The difference in background subtracted T cell response results on Day 8 and on Day 28 between MVA-NP+M1 and placebo will be analysed using an analysis of covariance (ANCOVA) model with treatment as factor, baseline as covariate and the interaction of both. Difference in LS means and corresponding 95% CI will be reported. This will be done separately for the vaccination and challenge period and for Day 8 and on Day 28. The same model will be repeated for the change from baseline in background subtracted T cell response results.

The difference in T cell response status on Day 8 and on Day 28 between MVA-NP+M1 and placebo will be analysed using a Fisher exact test.

The difference in antibody response results on Day 28 between MVA-NP+M1 and placebo will be analysed using an analysis of covariance (ANCOVA) model on the log-transformed results with treatment as factor and baseline as covariate and the interaction of both. Difference in LS means and corresponding 95% CI will be back-transformed to obtain the geometric mean ratio and corresponding 95% CI.

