Vaccination with MVA-NP+M1 results in a rapid increase in influenza-specific cross-reactive IFN- γ -secreting effector T cells which are maintained at protective levels over the course of a year [13]. In the older age groups, MVA-NP+M1 can boost pre-existing levels of influenza-specific T-cells and maintain them for up to 6 months post-vaccination [21]. MVA-NP+M1 in combination with licensed inactivated influenza vaccine induced influenza-specific T-cells and in addition, increase the magnitude and breadth of the antibody response induced by the inactivated influenza vaccine [22]. Furthermore, in a small Phase 2a challenge study of MVA-NP+M1 alone, MVA-NP+M1 vaccinated individuals experimentally challenged with live influenza virus tended to less severe symptoms and shorter duration of viral shedding compared to unvaccinated controls [23]. These studies demonstrated the safety of MVA-NP+M1 in older adults and in combination with seasonal influenza vaccine, the immunogenicity of MVA-NP+M1 in older adults and in combination with licensed inactivated seasonal

influenza vaccine and the potential efficacy of MVA-NP+M1 in limiting the severity of influenza illness in adults.

[H3N2] Challenge background

The A/Belgium [H3N2] challenge strain is a live, wild-type influenza A virus that was initially isolated from a nasopharyngeal swab from a paediatric patient in Antwerp, 2015. The first-in-human study was a non-controlled, open-label, single-centre, dose-escalation study to determine the safety, infectivity and immunology of the potential novel influenza virus H3N2 challenge strain. The primary objective was to determine the viral challenge strain dose that had an acceptable safety profile and an observed attack rate (on symptom and positive viral confirmation after day 2) of >60% (i.e. at least 8 out of 12 participants had to be infected). 36 participants were allocated to 3 cohorts. Each cohort consisted of 12 participants.

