3. STUDY DESIGN

3.1 OVERVIEW OF STUDY DESIGN

This is a randomized, single-centre, double blind study. The study will screen healthy volunteers and only enrol those with MNT <20. The study consists of an outpatient vaccination phase, and at least 6 weeks later an inpatient challenge phase.

155 participants will be randomized 3:2 to receive either MVA (N=93) or Placebo (N=62) by intramuscular injection in the non-dominant arm deltoid. Vaccination-related local and systemic symptoms will be followed by participant-directed diary cards for 7 days, and unsolicited adverse events will be followed throughout the study from consent signature. The vaccinations will be administered starting in April 2019. Blood for immunogenicity and storage of samples for correlates of protection will be drawn at five time points: Days 1, 8, 28 post-vaccination, on entry to the quarantine facility for challenge (Day -1), and 27 days post-challenge (Day 28).

Up to 20 participants with no intercurrent ILI will be challenged during each of the challenge periods lasting three weeks (approximately 12 MVA-NP+M1 recipients and 8 Placebo recipients per three-week block), to achieve a total of 80 participants from the MVA-NP+M1 group and 54 from the saline Placebo group being challenged. Participants will enter the quarantine facility on Day -2 or Day -1 and be discharged the morning of Day 11. The grouping of participants undergoing challenge will be as consistent as possible with the grouping used during the randomization process; i.e., the first participants vaccinated will be the first quarantined and challenged, but in all cases at least 6 weeks will have passed between vaccination and challenge.

Participants will receive a single intranasal administration of the H3N2 challenge agent (A/Belgium/4217/2015) as a nasal spray via the Teleflex MAD301 and MAD130. The MAD301 hard plastic atomizer will be combined with the MAD130 syringe and vial adaptor to constitute components that are the most similar to the VaxINator™ kit, used in previous studies for H3N2 inoculation.

Participants will be in a semi-recumbent (45°) position, lying in bed and will receive 0.25 mL of the challenge agent solution into each nostril.

After viral inoculation, participants are to remain in a supine position for 2 hours. Participants are not allowed to blow their noses during this period. All administrations will be performed by a member of the clinical site staff.

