2.2 IMMUNOGENICITY

2.2.1 Available data

T cell response is assessed using a double-colour enzymatic (DCE) ELISpot assay for IFN gamma and granzyme B on the peripheral blood mononuclear cell (PBMC)

SGS	Statistical Analysis Plan	
FLU010	Final analysis	Final 3.0 of 15JUN2020

samples, taken on day 0, day 8 and day 28 of the vaccination period and day -1 and day 28 of the challenge period. For each of IFN gamma and granzyme B, three stimulation antigens will be assessed: NP (4 pools), M1 (2 pools) and a negative control (DMSO). For each pool, the number of spot-forming colonies (SFC) per well (i.e. 200,000 cells) will be reported for two replicate wells.

ELISpot assay results will possibly not be available for the final analysis. In that case, analyses of the T cell response described below will not be done.

Antibody responses are evaluated with micro neutralization (MNT) and hemagglutination inhibition (HI) tests, done at screening (MNT only) and day -1 and day 28 of the challenge period.

2.2.2 *Derivation rules*

T cell response results will be averaged over all replicates within each pool, then background subtracted (set to 0 if negative) and finally added across all pools within each antigen as follows (XX being either NP or M1):

- Background subtracted T cell response result for pool Y of antigen XX (SFC/well) =
$$BG_{sub_{XX^Y}} = \text{average within pool Y of antigen XX} - \text{averaged negative control (DMSO) result}$$
- Background subtracted T cell response result for antigen XX (SFC/ 10^6 cells) =
$$BG_{sub_{XX}} = 5 \times \sum_{n=1}^k \max(BG_{sub_{XX^n}}, 0)$$

(k is the number of pools within the antigen XX)
- Background subtracted T cell response result for NP+M1 (SFC/ 10^6 cells) =
$$BG_{sub_{NP}} + BG_{sub_{M1}}$$

Negative control T cell response results will be averaged over all replicates and multiplied by 5 (to get SFC/ 10^6 cells).

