5.2 PHASES AND TIME POINTS

5.2.1 *Phases*

All events and assessments will be allocated to phases.

Phase	Start	End
Screening	Date of signing the ICF, with 00:00 added as time part	Vaccination date(time) – 1 minute
Vaccination	Vaccination date(time)	Challenge date(time) – 1 minute
Challenge	Challenge date(time)	End date of Day 28 post-challenge visit, with 23:59 added as time part
Follow-up	End of challenge phase + 1 minute	Date of last contact, with 23:59 added as time part

Per definition, and for each subject, the last available phase ends on the date of last contact (or the cut-off date for the topline analysis), with 23:59 added as time part.

AEs will be allocated to phases as described in section 3.1.2. All other assessments will be allocated to phases based on the assessment date(time).

In case of (partially) missing date(time) fields which cannot be allocated to a phase based on the available date(time) information, the visit label will be used to allocate to the correct phase. If this is not possible (unscheduled visits or visits on a turning point between phases), assessments will be allocated to the vaccination phase unless the available parts of the assessments start or stop date(time) provide evidence for allocating to the challenge/screening/follow-up phase.

5.2.2 *Baseline and change from baseline*

Baseline will be defined by phase.

The vaccination baseline value is the last available and non-missing value before the first administration of any study drug and will be used for data collected during the vaccination period.

The challenge baseline value is the last available and non-missing value before the administration of challenge inoculation and will be used for data collected during the challenge period.

Change from baseline is defined as follows:

Change from baseline at time point t = value at time point t – baseline value.

	Statistical Analysis Plan	
FLU010	Final analysis	Final 3.0 of 15JUN2020

5.2.3 *Relative day*

Relative days (DY) will be calculated both with respect to the vaccination and to the challenge, according to the following rule:

- Concerned date < reference date: DY = concerned date – reference date
- Concerned date \geq reference date: DY = concerned date – reference date + 1

The reference dates are the vaccination date and the date of challenge.

5.2.4 *Analysis visits*

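### The challenge-period T-cell ANCOVA adjusts for a pre-challenge value that vaccination is expected to have raised, so it does not estimate the between-arm difference that the SAP names

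*SAP*

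**What the plan says.** SAP 2.2.3 names the target as "The difference in background subtracted T cell response results on Day 8 and on Day 28 between MVA-NP+M1 and placebo". The method is an ANCOVA "model with treatment as factor, baseline as covariate and the interaction of both", reported as a difference in LS means with a 95% CI. On periods it says: "This will be done separately for the vaccination and challenge period and for Day 8 and on Day 28". It then adds: "The same model will be repeated for the change from baseline in background subtracted T cell response results".

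Which baseline applies is settled in SAP 5.2.2: "The challenge baseline value is the last available and non-missing value before the administration of challenge inoculation", to be used for data collected in the challenge period. SAP 2.2.1 gives the ELISpot schedule: "samples, taken on day 0, day 8 and day 28 of the vaccination period and day -1 and day 28 of the challenge period". So the challenge baseline for T cells is the Day -1 sample. No ELISpot sample is listed for challenge Day 8, so in the challenge period only Day 28 can be analysed.

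On timing, protocol 3.1 says that "in all cases at least 6 weeks will have passed between vaccination and challenge". On the expected effect of the vaccine by then, the protocol's background section describes induced influenza-specific T cells "which are maintained at protective levels over the course of a year", and the hypothesis in protocol 2.1 depends on that induction.

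**The concern.** In the vaccination period the covariate is measured before vaccination, so the ANCOVA is an ordinary randomised comparison. In the challenge period the same model conditions on a value measured after randomisation, which the treatment is meant to change. It then compares vaccinees and placebo recipients who have equal pre-challenge T cells. These are not like groups: a placebo recipient reaches a given level through natural memory alone, a vaccinee partly through the vaccine. Randomisation does not protect that comparison, and neither the protocol nor the SAP states it as a question.

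What is at stake is how the Day 28 post-challenge T-cell result is read. The protocol synopsis calls ELISpot the primary immune endpoint. A negative adjusted contrast could be reported as a weaker response to infection in vaccinees although the arms ended level. A real, lasting advantage could be reported as smaller than it is.

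**Working it through.** The documents give no SD, effect size, correlation or power for the T-cell comparison, so there is no planned figure to reproduce. The check is algebra, followed by a simulation under declared assumptions.

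**Inputs from the documents.** 80 MVA-NP+M1 and 54 placebo participants challenged (SAP 1.2); model and target (SAP 2.2.3); covariate (SAP 5.2.2, 2.2.1); two-sided 0.05 (SAP 2.1.3). SAP 9.1 has no code for this model, so LS means are taken at the pooled mean of the covariate, the usual default.

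**Assumed inputs**, in within-arm SD units: Day -1 shift d due to vaccine = 0, 0.5 or 1.0; correlation rho between any two of the pre-vaccination, Day -1 and Day 28 values = 0.3, 0.5 or 0.7; normal data with unit SD, so the slope equals rho.

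**Step 1: what the contrast estimates.** Let D be the true Day 28 difference. At the pooled covariate mean, the vaccine arm is moved down by (54/134) × d and the placebo arm up by (80/134) × d, each along its own slope. Hence

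expected contrast = D − s × d, with s = (54 × vaccine-arm slope + 80 × placebo-arm slope)/134.

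The interaction term turns s into a weighted average of the two slopes. It does not remove the subtraction.

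**Step 2: the change-from-baseline model.** Subtracting the Day -1 value from the outcome lowers both arms' slopes by 1 and leaves the treatment and interaction coefficients as they were. The contrast is identical, and it was identical in every simulated case.

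**Step 3: one case by hand.** Take D = 0, d = 0.5, rho = 0.5. The contrast is 0 − 0.5 × 0.5 = −0.25. The residual variance is 1 − 0.25 = 0.75. The covariate offsets are 54/134 × 0.5 = 0.2015 and 80/134 × 0.5 = 0.2985. The variance is 0.75 × (1/80 + 1/54 + 0.2015²/79 + 0.2985²/53) = 0.75 × 0.0332 = 0.0249, so the SE is 0.158. The ratio 0.25/0.158 is 1.58, against a critical value of 1.98 on 130 df. The chance of a significant negative result is about 35%, which agrees with the simulation below.

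**Step 4: simulation** (4,000 trials per case). Significant means p < 0.05, that is, a 95% CI excluding zero.

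| rho | d | Arms equal at Day 28 (D = 0): estimate | significant | Full persistence (D = d): estimate | significant |
|---|---|---|---|---|---|
| 0.3 | 0.5 | −0.15 | 14% | 0.35 | 52% |
| 0.5 | 0.5 | −0.25 | 35% | 0.25 | 36% |
| 0.7 | 0.5 | −0.35 | 76% | 0.15 | 20% |
| 0.3 | 1.0 | −0.30 | 33% | 0.70 | 95% |
| 0.5 | 1.0 | −0.50 | 82% | 0.50 | 81% |
| 0.7 | 1.0 | −0.70 | 99.8% | 0.30 | 53% |

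With full persistence of 0.5 SD, an unadjusted t-test has about 80% power. When D equals exactly rho × d, the SAP contrast averages about zero and is significant in about 5% of trials. With d = 0 the SAP model behaves properly (4.7% to 5.2%).

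**Step 5: the pre-vaccination value as covariate.** With D = 0, the mean bias is at most 0.003 SD and the rejection rate 4.6% to 5.6%. With D = d = 0.5, the estimate is 0.50 SD and the power 83%, 89% and 98% for rho 0.3, 0.5 and 0.7.

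**The case against.** The strongest reply is that SAP 5.2.2 sets baselines by phase on purpose, so the challenge-period model asks how participants respond to challenge given where they started. If vaccinees start higher and both arms end level, their smaller rise is real. That is a legitimate question, and a negative contrast would be a fair answer to it. But SAP 2.2.3 does not pose it: it names a difference between arms, and nothing says that the adjusted contrast is conditional and not protected by randomisation.

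The reply also limits how far the point goes, and these limits stand:

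- A reader might infer that the model makes a true persisting difference vanish. That happens only when the difference equals slope times the Day -1 shift. Full persistence, the case nearest to the protocol's own expectation, gives attenuation.
- A reader might take 14% to 99.8% as this trial's error rate. It is not. The range follows from assumed shifts and correlations, from normal data where the real results are counts floored at zero, and from a challenge that fully erases the Day -1 difference.
- The unadjusted picture will be visible. SAP 2.2.4 and 5.4.1 give descriptive results by visit with CIs on medians, and SAP 2.2.3 has an unadjusted Fisher test of responder status. They would help a careful reader, but they do not correct the reported LS-mean difference and its CI.
- Protocol 9.1.2.3 places this comparison among exploratory endpoints, and SAP 2.2.1 allows that ELISpot results may not be available for the final analysis.
- Protocol 9.1.2.3 foresaw a t-test or Mann-Whitney U test, but names no visit and leaves detail to the SAP. That departure alone proves little.

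**Conclusion.** The point holds for one analysis: the Day 28 post-challenge T-cell ANCOVA and its change-from-baseline twin. Its LS-mean difference estimates the Day 28 difference minus slope times the Day -1 difference. The direction of the error needs only two conditions: the vaccine raises the Day -1 value, as the protocol expects, and that value predicts Day 28 positively within arms. The size depends on assumptions the documents cannot settle. Over the range assumed here, the contrast is too low by 0.15 to 0.70 SD. If the vaccine no longer affected the Day -1 value, there would be no bias.

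A wider reading, that the trial's efficacy conclusion or its immunogenicity analysis as a whole is compromised, is not supported. The primary vAUC test, the vaccination-period ANCOVA and the descriptive T-cell tables are untouched. The change is worth making before the result is interpreted, but it concerns an exploratory analysis.

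**What to change.** In SAP 2.2.3, state that the between-arm comparison of T-cell response at Day 28 after challenge uses the pre-vaccination value as covariate (Day 1 in the schedule, day 0 in SAP 2.2.1), and record this as an exception to the baseline rule in SAP 5.2.2. That sample is already collected and already serves the vaccination-period model.

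If the Day -1-adjusted model is kept, label it an exploratory, non-randomised analysis of response to challenge given the pre-challenge level. Do not present the challenge-period ANCOVA on change from baseline as separate confirmation, because its treatment contrast is the same number.

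The cost is a short SAP edit, a change of covariate in the program and, if the conditional model stays, one extra model to report. The real downside is that the formal analysis of the rise after challenge becomes less prominent. The rise remains in the tables of change from baseline by arm.

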2.2.4 Presentation of results

To assess the impact of missing DMSO replicates, all tables and figures on T-cell response will be prepared on two subsets of data (evaluated separately for NP and M1):

- Samples with at least 1 result
- Subset above, excluding samples with only 1 DMSO replicate result

Background subtracted and negative control T cell response results (IFN-gamma and granzyme B results; separately for NP, M1, NP+M1) will be summarised by means of descriptive statistics at each analysis visit. This will be done separately for the vaccination and challenge period. Actual values and changes from baseline will be tabulated separately.

T cell responder status will be presented in a frequency table at each analysis visit, separately for vaccination and challenge period.

Antibody response results will be summarised by means of descriptive statistics at each analysis visit. Actual values and changes from baseline will be tabulated separately. The ratio (MVA-NP+M1 / placebo) of the geometric means will also be shown with corresponding 95% CI.

Correlation of T cell responses, as assessed by the mean increase from baseline to post vaccination at day 8 and day 28 (for IFN-gamma and granzyme B results; separately for NP, M1, NP+M1), to the primary endpoint, symptom scores, and influenza incidence will be explored graphically, including Spearman correlation coefficients.

Graphs of the median actual values over time will be prepared for background subtracted and negative control IFN-gamma and granzyme B results (separately for NP, M1, NP+M1).

	Statistical Analysis Plan	
FLU010	Final analysis	Final 3.0 of 15JUN2020

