In situations where individuals are exposed to a newly arisen influenza virus strain against which they lack protective neutralising antibodies, cross-reactive T-cells against conserved internal antigens of influenza have been shown to be associated with limiting viral shedding, reduced duration of symptoms and minimising severity of symptomatic illness [10, 11]. Thus, a vaccine against influenza that induced protective T cell responses against conserved internal antigens could provide lasting immunity against not only human seasonal influenza, but also

other subtypes currently found in avian species or swine which have the potential to cause a new pandemic. Since adults have been primed by prior exposure to influenza, a vaccine expressing conserved internal antigens of influenza such as NP and M1 could be used to boost cross-reactive T-cell responses to protective levels, providing durable broad immunity to all subtypes of influenza A.

The internal proteins of the influenza virus are more conserved compared to the external surface glycoproteins. There are two reasons for selecting NP and M1 as a target for T-cell inducing vaccines. First, there is very little polymorphism of NP and M1 between influenza A isolates. NP is 92% identical between H3N2 and H1N1 strains, and 91% identical between H3N2 and H5N1 strains. M1 is 95% identical between H3N2 and H1N1 strains, and 93% identical between H3N2 and H5N1 strains. This low level of variation appears to allow strong T cell cross-reactivity. In the local population more than 70% of individuals generate a T cell response to these two antigens [12]. Second, analysis of T-cell response to all the proteins of influenza have shown that the T-cell response to NP and M1 is the strongest and 80% of individuals have responses to these two proteins (Figure 1). Furthermore, recent studies have shown that T-cells specific to M1 and NP are associated with protecting individuals against influenza by limiting viral shedding, reduced duration of symptoms and minimising severity of symptomatic illness [10, 11].

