2.2 SECONDARY OBJECTIVES

Secondary objectives are to determine:

- The incidence in each group (MVA-NP+M1 and saline Placebo) of laboratory-confirmed influenza (qPCR or culture) (and time to start; time to peak and duration of qPCR and quantitative culture results)
- The attack rate, defined as percentage of inoculated participants with at least two positive swabs as determined by qPCR
- Total AUC for total symptom score for MVA-NP+M1 vs. Placebo
- Total days of fever for MVA-NP+M1 vs. Placebo
- Total mucus weight for MVA-NP+M1 vs. Placebo
- Correlation of T cell responses (as defined by ELISpot assay) to the primary endpoint, symptom scores, and influenza incidence
- Safety of MVA-NP+M1 vaccination
- Safety of H3N2 challenge in the setting of MVA-NP+M1 vaccination

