7.1 TIMING OF ASSESSMENTS

An overview of the timing of treatment(s) and assessments is given in the Time and Events Schedule of the vaccination period as well as for the challenge phase.

A 10% deviation from theoretical post dose times will be allowed for all post-dose assessments. The windows for follow-up visits post-vaccination will be 7 ± 1 day, 27 ± 3 days, 55 ± 3 days, day from vaccination to challenge

> 6 weeks, but less than 6 months. The windows for follow-up visits post-challenge confinement period will be 27 ± 3 days and/ or 6 months post-vaccination (180 ± 14 days) whichever is longer.

7.1.1 *Screening Period*

Screening

Screening for eligible and consenting participants will be performed within approximately 6 weeks prior to randomization/the first administration of study drugs. It will be possible to include participants who are screened with the appropriate MNT assay from another protocol or screening test, but the test needs to be performed or repeated within 6 weeks of vaccination.

Some eligibility criteria will be checked prior to assessing MNT in the study. These criteria involve:

- life style questions i.e. smoking, contraception, identify current BMI (upon Investigator discretion), recent or planned participation in other studies etc. [inclusion criteria 1 to 4 and exclusion criteria 1 & 7].
- current illnesses including current medication.

Any physical examination, vital signs and laboratory assessments will be completed at Screening 2 visit within the 3 weeks leading to the vaccination once MNT is confirmed. However, in order to ensure a sufficient number of participants are vaccinated in a given group, MNT may be performed at Screening 2 at the same time as Screening 2 assessments.

Participants will be given a full explanation of the nature of the study and written informed consent (approved by the local ethics committee) will be obtained according to local requirements before any study-related assessment is carried out.

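### The planned T-cell correlations use only the Day 8 and Day 28 rise; the pre-challenge level, already measured, is never related to shedding, symptoms or influenza incidence

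*SAP*

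**What the plan says.** Protocol 2.2 lists as a secondary objective: "Correlation of T cell responses (as defined by ELISpot assay) to the primary endpoint, symptom scores, and influenza incidence". It fixes no time point and does not limit the response to a rise. Protocol 9.1.2.3 adds that an exploratory correlate-of-protection analysis will be set out in the SAP.

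The SAP's answer is in section 2.2.4: "Correlation of T cell responses, as assessed by the mean increase from baseline to post vaccination at day 8 and day 28". Both readouts (granzyme B and IFN-gamma) are covered, each by antigen and for the two antigens combined. The relation to the primary endpoint, symptom scores and influenza incidence "will be explored graphically, including Spearman correlation coefficients". Figure 14.2.4.1 in SAP 8.3 is the matching display. It names the ITT set and gives no time point. No other correlate analysis appears in the SAP.

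SAP 2.2.1 says the ELISpot samples are "taken on day 0, day 8 and day 28 of the vaccination period and day -1 and day 28 of the challenge period". Protocol 3.1 counts the draw on entry to quarantine among those taken for immunogenicity and correlates of protection; the Time and Events Schedule allows it on Day -2 or Day -1. Protocol 7.1 sets the time from vaccination to challenge at "> 6 weeks, but less than 6 months".

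**The concern.** The protocol's rationale (section 1.1) is that the vaccine "could be used to boost cross-reactive T-cell responses to protective levels, providing durable broad immunity". That is an argument about how many cross-reactive T cells a person has when exposed. The correlated variable is a different quantity: the change measured one and four weeks after vaccination. Three things separate the two.

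- **Time.** Responses may wane between Day 28 and challenge, and the interval varies between participants.
- **Pre-existing immunity.** Protocol 1.1 reports NP and M1 responses in more than 70% of the local population and, in a second statement, in 80% of individuals. A change score takes the pre-vaccination level out.
- **Placebo recipients.** Barring intercurrent exposure their true rise is zero, so within that arm the rise is mostly assay noise, although their natural T-cell levels vary and could relate to shedding.

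At stake is the reading of a flat plot. It could be reported as showing no T-cell correlate when the level at exposure had never been examined against outcome.

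**Working it through.** The documents give no expected coefficient, power or sample size for this analysis, so there is no planned figure to reproduce.

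**1. Where the pre-challenge ELISpot value is used.** It enters the descriptive tables by visit, the responder tables and the median plots (SAP 2.2.4), the individual plots (Figure 14.2.4.3) and Listing 16.2.6.5. As challenge baseline (SAP 5.2.2) it is also a covariate in the challenge-period ANCOVA of T-cell response (SAP 2.2.3). None of these relates it to vAUC, symptoms or incidence.

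**2. Age of the Day 28 rise at inoculation.** Inputs from Protocol 7.1: Day 28 visit at 27 ± 3 days after vaccination; challenge between 6 weeks (42 days) and 6 months (taken as 180 days, the protocol's own Month 6 figure).

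- Shortest: 42 − 27 = 15 days (42 − 30 = 12 with the visit window).
- Longest: 180 − 27 = 153 days (180 − 24 = 156 with the visit window).

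**3. What a weaker proxy would cost (illustration).** Suppose the pre-challenge level has Spearman correlation ρ with vAUC, and the rise correlates r with that level and acts only through it. The rise then shows ρ × r. The chance of a coefficient distinguishable from zero, two-sided 0.05, is approximately Φ(d − 1.96), with d = atanh(ρr) / √(1.06/(n − 3)). The SAP plans no test here; this only expresses the attenuation. ρ and r are assumptions. With ρ = 0.3 in the 80 vaccinees, √(1.06/77) = 0.117:

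| Measure | Expected coefficient (absolute) | d | Chance |
|---|---|---|---|
| Pre-challenge level | 0.30 | 2.64 | 75% |
| Rise, r = 0.8 | 0.24 | 2.09 | 55% |
| Rise, r = 0.6 | 0.18 | 1.55 | 34% |
| Rise, r = 0.4 | 0.12 | 1.03 | 18% |

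**4. How far this depends on assumptions.** Expected within-vaccinee Spearman coefficients were simulated on the SFC scale, with the rise as post minus baseline. Assumptions: baseline SD 0.5, assay SD 0.15, boost mean 0.6 and SD 0.3 (all log10), boost independent of baseline, challenge at 43 to 180 days, latent correlation 0.42 with whatever drives vAUC. The three values are for boost half-lives of 40, 90 and 365 days.

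| What drives vAUC | Day 8 rise | Pre-challenge level |
|---|---|---|
| T-cell level at challenge | −0.28 / −0.32 / −0.34 | −0.38 / −0.38 / −0.37 |
| Vaccine-induced part still present | −0.15 / −0.18 / −0.21 | −0.08 / −0.11 / −0.14 |

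Within placebo, if the level drives vAUC, the rise gives 0.00 and the level −0.33 to −0.38.

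A second simulation also let the level drive vAUC but took the rise on the log scale (|ρ| = 0.3, 60% of the boost retained, assay SD 0.12). As baseline SD went from 0.15 to 0.3 to 0.5, the chance of detection in vaccinees was 31%, 18% and 12% with the rise, against 65%, 69% and 74% with the level. The loss thus ranges from modest to large, and the ranking reverses if only induced cells matter.

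**The case against.** The strongest reply is that the rise is the right measure. The primary hypothesis (Protocol 2.1) concerns T cells induced by the vaccine, and a rise measures induction. If induced cells drive protection, the rise does better than the level (step 4). Protocol 1.1 also reports responses maintained over a year, and for up to 6 months in older adults, so the Day 28 value may track the pre-challenge value closely. Fast-waning scenarios sit poorly with that. All of this stands. It argues for keeping the rise, but not for leaving the level out.

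The analysis is also graphical, has no decision rule, and will not be run if ELISpot results are unavailable (SAP 2.2.1). That limits the consequence.

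Three stronger readings are tempting, and the documents do not support them.

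- **That the SAP pools the arms.** No text says so. SAP 5.4.2 lists treatment labels for figures and reserves the overall category for general characteristics and adverse events, which points to display by arm. How the coefficient is computed is simply not stated.
- **That the 54 placebo recipients, 40% of the 134 challenged, carry no information.** This holds only for a rise examined within the placebo arm. In a pooled coefficient they would form the low end of the rise, though that coefficient would mix the arm difference with any individual-level association.
- **That the pre-challenge level should replace the rise as the main variable.** That depends on biology the trial has yet to establish.

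**Conclusion.** The concern holds as an omission that is cheap to repair. The SAP relates outcome only to the Day 8 and Day 28 rise. The level at exposure is measured by the same assay, on a draw the protocol takes for correlates of protection, yet it is tabulated and plotted without being related to any outcome. A true link between T cells present at challenge and shedding could therefore be missed.

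The gap of about 15 to 153 days between the Day 28 sample and inoculation follows from the protocol. The size of the loss does not: the simulated figures rest on assumed boost variability, waning, assay error and driver of protection. A reader might take them as an estimate of lost power, but they show only direction and range. The loss may be small if responses persist. The primary efficacy test is untouched.

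**What to change.** In SAP 2.2.4 and Figure 14.2.4.1, keep the Day 8 and Day 28 rises and add beside them:

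- the background-subtracted NP, M1 and NP+M1 level on the pre-challenge (Day -2 or Day -1) sample;
- the change from vaccination baseline to that sample, which speaks to the induction hypothesis at the time of exposure.

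State that Spearman coefficients are given within each arm and, if an overall value is shown, make it arm-stratified (partial). State also whether the Day 8 and Day 28 increases are averaged or correlated separately, since the present wording allows either.

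The cost is a few sentences of SAP text and some extra panels, with no new samples or assays. The downside is more exploratory coefficients without multiplicity control, which a sentence in the report can acknowledge.
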